### 8.3.1 SPECT/CT Scans

- SPECT/CT scan will be used to evaluate the radiation dosimetry of [In]-FPI-2107 and make projections for [Ac]-FPI-2068 and the effect of predose administration of FPI-2053 on radiation dosimetry.
- SPECT/CT scan will also be used to determine eligibility for treatment with [Ac]-FPI-2068.
- Two SPECT/CT images will be obtained between 24 and 96 hours post-[In]-FPI-2107 injection; please refer to the Site Imaging Manual for timing of the scans, as precise timing may be revised over the course of the study.

### 8.3.2 Whole Body Planar Scintigraphy

- Planar imaging must be used to evaluate the radiation dosimetry of [In]-FPI-2107 and [Ac]-FPI-2068 and the effect of predose administration of FPI-2053 on radiation dosimetry.
- Four planar images will be obtained between 0 and 96 hours post-[In]-FPI-2107 injection; please refer to the Site Imaging Manual for timing of the scans, as precise timing may be revised over the course of the study.

## 8.4 Safety Assessments

Planned time points for all safety assessments are provided in the SoAs (see Section 8.1).

### 8.4.1 Physical Examinations

Physical examination will be performed at timepoints as specified in the SoAs (see Section 8.1). Situations in which physical examination results should be reported as AEs are described in Section 8.5.5.

- A complete physical examination will include assessments of the following; general appearance, respiratory, cardiovascular, abdomen skin, head, and neck (including ears, eyes, nose, and throat), lymph nodes, thyroid, muscular-skeletal (including spine and extremities), and neurological systems, and weight.
- A symptom-directed examination will include assessments of relevant organ systems related to any AE that the participant may be experiencing, as deemed appropriate by the Investigator.

- Height will be measured at screening only.
- Weight will be measured as part of complete physical examinations in addition to other timepoints outlined in the SoAs (see Section 8.1).

#### **8.4.2 Vital Signs**

Vital signs (body temperature, blood pressure, respiration rate, and heart [pulse] rate) will be performed at timepoints specified in the SoAs (see Section 8.1). Situations in which changes in vital signs should be reported as AEs are described in Section 8.5.5.

#### **8.4.3 Electrocardiograms**

All ECGs will be performed in triplicate (all 3 within a 5-minute time period, at least 1 minute apart) and the mean value of the triplicate measurement will be recorded as the baseline value.

All ECG recordings will be made with the participant in a supine position having rested in this position for at least 5 minutes before the start of the ECG.

All ECGs will be recorded at a speed of 25 mm/second with amplitude recording of 100 mm/mV. At least 3 full complexes must be recorded. A multi-channel ECG machine should be used (equals 3 leads recorded simultaneously) and there must be amplitude index calibration for each lead. Digital copies of ECGs may be held centrally by a central ECG provider and stored for potential independent analysis during, or at the end of, the study at the Sponsor's discretion. The central independent review will not replace the local review by the Investigator or other medically qualified designee.

Electronic software will be used to assess the following parameters: pulse rate, QRS, QT, and QTc time intervals (to be reported by Fridericia's formula [QTcF], where available, or by Bazett's formula [QTcB], where QTcF is not available) should be reported if available. All ECGs must be reviewed by the Principal Investigator or a medically qualified designee before the start of injection or infusion (for time points prior to the start of injection or infusion) and before the participant is permitted to leave the clinic (for post injection or infusion time points). In case of a clinically significant ECG abnormality (e.g., occurrence of de- or re-polarisation disorders, arrhythmic disorders), including QTcF prolongation of >500 milliseconds, a minimum of 2 additional 12-lead ECGs should be obtained over a brief interval (e.g., 30 minutes) to confirm the abnormality based on manual over-read by a medically qualified person. Such abnormalities and any obvious changes in ECG parameters from baseline will be assessed by the Principal Investigator for clinical significance. If clinically significant, the ECG abnormality should be recorded as an AE in the eCRF. Clinical interpretation and any associated management of participant related to ECG abnormalities will be done locally and will be based on interpretation by a medically qualified person at the site.

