**Objectives and Endpoints:**

**Table 1      Objectives and Endpoints**

Type	Objectives	Endpoints
Primary		
Safety / Dosimetry	
 
Evaluate the safety, tolerability, and dosimetry of [In]-FPI-2107, FPI-2053, and [Ac]-FPI-2068
 
Determine the RP2D of [Ac]-FPI-2068, given with or without FPI-2053
 
	
 
Frequency, duration, and severity of AEs, DLTs, and changes in clinical, laboratory, and ECG parameters compared to baseline
 
Estimates of residence time and absorbed radiation doses to the whole body, organs, and selected regions of interest for [In]-FPI-2107 and [Ac]-FPI-2068
 

Dosimetry	
 
Determine the effect of predose administration of FPI-2053 on the radiation dosimetry of [In]-FPI-2107 (whole body, organs, and selected regions of interest)
 
Estimate the effect of predose administration of FPI-2053 on the radiation dosimetry of [Ac]-FPI-2068 (whole body, organs, and selected regions of interest)
 
	
 
Changes in uptake of [In]-FPI-2107 and projected RAD of [Ac]-FPI-2068 by imaging following predose administration of FPI-2053 compared to uptake of [In]-FPI-2107 imaging alone
 

Secondary		
Efficacy	
 
Assess preliminary anti-tumour activity of [Ac]-FPI-2068
 
	
 
ORR per RECIST 1.1
 
TTR, DoR, PFS, DCR, and OS.
 
Percentage change in total ctDNA (VAF) compared to baseline
 

Pharmacodynamics	
 
Obtain preliminary data on the tumour uptake of [In]-FPI-2107
 
	
 
Tumour uptake of [In]-FPI-2107 in selected regions of interest on SPECT/CT and/or planar images
 

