All safety data including safety laboratory values, vital signs, and ECG data will be listed individually by subject and appropriately summarised. For all laboratory variables that are included in the current version of CTCAE, the CTCAE grade will be calculated. Details of any deaths will be listed for all participants. Graphical presentations of safety data will be presented as appropriate. DLTs will be displayed in a listing.

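### The Bazett fallback for QTc lets two correction scales into one ECG variable, although every QTc criterion in the protocol is stated in QTcF

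*Protocol*

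**What the plan says.** Protocol Section 8.4.3 names the ECG parameters: "Electronic software will be used to assess the following parameters: pulse rate, QRS, QT, and QTc time intervals". The same sentence then fixes how QTc is chosen: by Fridericia's formula where that can be had, and otherwise by Bazett's "formula [QTcB], where QTcF is not available) should be reported if available". ECGs are taken in triplicate, and "the mean value of the triplicate measurement will be recorded as the baseline value".

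The section does not require that the formula used at baseline be used again later, or that sites contributing to the same dose level use the same one. It does not ask for QTcF to be calculated where the software does not print it.

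The numeric QTc criteria are all on the Fridericia scale. Inclusion criterion 10b (Section 5.1) sets QTcF limits of 450 ms for men and 470 ms for women. The trigger for repeat ECGs in Section 8.4.3 is worded "including QTcF prolongation of >500 milliseconds".

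The primary safety endpoint in Tables 1 and 6 includes "changes in clinical, laboratory, and ECG parameters compared to baseline". For the analysis, Section 9.4.3 says: "All safety data including safety laboratory values, vital signs, and ECG data will be listed individually by subject and appropriately summarised". Section 9.4.1 has summaries presented by cohort and/or dose level.

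**The concern.** The two formulas agree only at 60 bpm. Away from that rate the same tracing gives two different QTc values, and under this rule the one that is reported depends on what the local software prints. If the formula changes between a participant's baseline and a later ECG, the change from baseline contains a part that has nothing to do with the drug. If it differs between participants in the same dose level, the summary pools two scales.

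The study is first-in-human, multicentre and uses small groups: about three participants per Part A cohort and three to nine evaluable per Part B dose level. One participant's formula can therefore visibly move a cohort mean. Where only QTcB is reported, the site also has no limit on the matching scale for criterion 10b or for the repeat-ECG trigger.

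**Working it through.** The protocol states no figure for this effect, so there is none to reproduce. The check is algebra on the two standard formulas.

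**Inputs from the protocol:** the fallback rule, and QT and pulse rate as assessed parameters (Section 8.4.3); the cohort size of about three in Part A (Section 9.2).

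**Assumed, not in the protocol:** heart rates of 50 to 100 bpm and a true QTcF of 380 to 450 ms.

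**Formulas**, with RR = 60/HR in seconds:

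- QTcF = QT/RR^(1/3)
- QTcB = QT/RR^(1/2)
- QTcB/QTcF = RR^(−1/6) = (HR/60)^(1/6)
- QTcB − QTcF = QTcF × ((HR/60)^(1/6) − 1)

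**One tracing.** QT 360 ms at 80 bpm has RR = 0.75 s. QTcF = 360/0.75^(1/3) = 396 ms and QTcB = 360/0.75^(1/2) = 416 ms. The difference is about 19.5 ms from the same ECG.

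**Difference QTcB − QTcF in ms:**

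| HR (bpm) | QTcF 380 | QTcF 400 | QTcF 420 | QTcF 450 |
|---|---|---|---|---|
| 50 | −11.4 | −12.0 | −12.6 | −13.5 |
| 60 | 0 | 0 | 0 | 0 |
| 65 | +5.1 | +5.4 | +5.6 | +6.0 |
| 70 | +9.9 | +10.4 | +10.9 | +11.7 |
| 75 | +14.4 | +15.2 | +15.9 | +17.1 |
| 80 | +18.7 | +19.6 | +20.6 | +22.1 |
| 90 | +26.6 | +28.0 | +29.4 | +31.5 |
| 100 | +33.8 | +35.5 | +37.3 | +40.0 |

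**Effect on a small cohort.** Take three participants with a true QTcF of 400 ms and no drug effect, one of whom has QTcF at baseline and QTcB later. The mean change moves by 19.6/3 = 6.5 ms at 80 bpm and 35.5/3 = 11.8 ms at 100 bpm. At 65 to 75 bpm it moves by 5.4/3 = 1.8 to 15.2/3 = 5.1 ms.

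**Recovering QTcF.** From QT and heart rate, use the first formula. From QTcB and heart rate, QTcF = QTcB × (60/HR)^(1/6). For the tracing above, 416 × 0.75^(1/6) returns about 396 ms. Once every value is on the QTcF scale, the artefact from switching formula is 0 ms at any heart rate.

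**The case against.** The strongest reply is that Section 8.4.3 is a reporting rule. It labels QTcF and QTcB separately, nowhere tells anyone to subtract a QTcF baseline from a QTcB value, and Section 9 leaves detailed methods to the SAP, which may keep one formula per summary. That stands as far as it goes: the protocol permits the mixing but does not prescribe it. A reader might infer that the primary endpoint mixes two scales by design, and the documents do not say so. It does not dispose of the point, because the fallback itself is fixed in the protocol and governs what sites report and read locally.

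Three other readings are tempting and unsupported:

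- **A breach of the entry limit.** A man with QTcF 420 ms at 100 bpm has a QTcB of 457 ms. Setting that against 450 ms compares a Bazett value with a Fridericia limit. Criterion 10b is written in QTcF, so this is not a breach of it.
- **Inflated counts above QTc thresholds.** The protocol plans no such count.
- **QTcF can always be derived.** The sentence ends with a proviso on availability, so a complete QT and heart-rate pair is not guaranteed for every ECG.

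The protocol also has safeguards. ECGs are recorded supine after rest, so heart rates may lie towards the lower end of the table. Each ECG is reviewed by a medically qualified person, clinically significant abnormalities need repeat ECGs with manual over-read, and digital copies may be held centrally. These reduce the chance that a spurious value becomes an adverse event, but they do not put reported values on one scale.

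**Conclusion.** The point holds as a fault in a stated rule, with limited reach. Section 8.4.3 allows two scales in one variable, while the eligibility limits and the confirmation trigger use only one of them.

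The size depends on heart rate, which the protocol does not give. For a QTcF of about 400 ms it runs from about −12 ms at 50 bpm (false shortening), through 0 at 60 and +5 to +15 at 65–75, to +20 to +36 at 80–100 bpm. The upper figures should not be read as typical. The full shift appears in a participant's change from baseline only if the formula switches. With Bazett at both visits and an unchanged heart rate there is no switch artefact, although summaries may still pool that participant with others on QTcF.

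The effect stays within descriptive safety summaries and local assessment of change from baseline. Section 9.1 states no hypotheses, the DLT list in Section 6.7.7.1 names no QTc value, and mTPI-2 decisions rest on DLT counts. The change is still worth making because the parameters needed are already among those assessed.

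**What to change.** Replace the Bazett fallback in Section 8.4.3 with:

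> QTcF will be derived as QT/RR^(1/3) (RR = 60/heart rate, in seconds) from the recorded QT and heart rate wherever the machine does not print it, or from QTcB and heart rate as QTcB × (60/HR)^(1/6) if QT is not recorded. All summaries, changes from baseline and the existing QTcF criteria use QTcF only. Any QTcB that cannot be converted is listed separately and not pooled.

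The cost is this short replacement text and one derived variable. It needs no new data collection, does not depend on the optional central ECG storage, and leaves every clinical limit and management step as written.

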#### **8.4.4 Clinical Safety Laboratory Assessments**

Blood and urine samples for assessment of haematology, clinical chemistry, coagulation,

thyroid function, pregnancy test, and urinalysis will be taken at the visits indicated in the SoA (see Section 8.1).

Additional safety samples may be collected, if clinically indicated, at the discretion of the Investigator. The date, time of collection, and results (values, units and reference ranges) will be recorded on the appropriate eCRF.

The clinical chemistry, haematology, coagulation, and urinalysis will be performed at a local laboratory at or near to the Investigator site. Sample tubes and sample sizes may vary depending on laboratory method used and routine practice at the site.

The following laboratory variables will be measured.

**Table 29      Laboratory Safety Variables**

Assessment group	Variables	
Haematology (whole blood)	Hb	Platelet count
	Haematocrit	Reticulocytes
	RBC count	WBC count with differential (neutrophils, lymphocytes, monocytes, eosinophils, and basophils)
	Blood smear (pathology, only during the End of Treatment and Extended Follow-up period)	
Clinical chemistry (serum or plasma)	Sodium	ALP a
	Potassium	LDH
	Chloride	GGT
	Bicarbonate	Total protein
	BUN	Albumin
	Serum creatinine	Calcium
	Glucose	Magnesium
	Total bilirubin a, b, c	Phosphate
	AST a, b	Amylase
	ALT a, b	Lipase
Coagulation	PT	aPTT
	INR	
Thyroid panel	Free T3	Free T4
	TSH	
Pregnancy test (blood or urine in accordance with institutional practice)	hCG or beta hCG	
Urinalysis (including dipstick)	U-Hb/erythrocytes/blood	U-pH
	U-protein/albumin	U-bilirubin

Assessment group	Variables	
	U-glucose	U-ketones
	U-microscopy including WBC/HPF and RBC/HPF d	

ALP, alkaline phosphatase; ALT, alanine aminotransferase; aPTT, activated partial thromboplastin time; AST, aspartate aminotransferase; BUN, blood urea nitrogen; Hb, haemoglobin; hCG, human chorionic gonadotropin; GGT, gamma-glutamyl transferase; HPF, high-power field; INR, international normalised ratio; LDH, lactate dehydrogenase; PT, prothrombin time; PTT, partial thromboplastin time; RBC, red blood cell; T3, triiodothyronine; T4, thyroxine; TSH, thyroid stimulating hormone; U, urine; ULN, upper limit of normal; WBC, white blood cell.

a Tests for AST, ALT, ALP, and total bilirubin must be conducted and assessed concurrently.

b In case a participant shows an AST **or** ALT  $\geq 3 \times$  ULN together with total bilirubin  $\geq 2 \times$  ULN please refer to [Appendix E](#) (Actions required in cases of increases in liver biochemistry and evaluation of Hy's Law'), for further instructions.

c If total bilirubin increases  $1.5 \times$  above the ULN (or  $2 \times$  above the baseline value in participants with documented Gilbert's syndrome), indirect bilirubin should be measured and any potential alternative aetiologies should be assessed.

d If clinically indicated.

#### 8.4.5 ECOG Performance Status

ECOG PS will be assessed as stated in the SoAs, based on ECOG scale.

#### 8.4.6 Other Safety Assessments

##### 8.4.6.1 Pneumonitis/ILD Investigation

If new or worsening pulmonary symptoms (e.g., dyspnoea, cough or fever) suggestive of ILD/pneumonitis is observed, treatment with study intervention must be interrupted and a thorough investigation is required as described in detail in the toxicity management guidelines (TMGs) for [Ac]-FPI-2068 (see [Table 15](#)).

Evaluations could include:

- History (cough, shortness of breath, pyrexia) and examination (auscultation of lung fields)
- Tests to rule out infection
- Tests to rule out a cardiac event (ECG and troponin)
- High resolution CT (HRCT) scan of the chest
- Pulmonary function tests (spirometry, diffusing capacity of the lung for carbon monoxide) and pulse oximetry (SpO2)
- Arterial blood gases if clinically indicated
- Pulmonologist consultation
- Bronchoscopy and bronchoalveolar lavage as clinically indicated and if feasible
- One blood sample for PK as soon as ILD/pneumonitis is suspected (Section [8.7.1](#))
- Additional blood samples for exploratory ILD biomarker analysis as soon as ILD/pneumonitis is suspected, if feasible (Section [8.8.2.3](#))

- Other tests/procedures could be considered, as clinically indicated, and to rule out alternate aetiology such as infection (e.g., lung biopsy if clinically indicated and feasible without additional harm to the wellbeing of the participant).

The results of the full diagnostic workup (including HRCT, blood and sputum culture, haematological parameters, etc.) must be captured in the eCRF. It is strongly recommended to perform a full diagnostic workup to exclude alternative causes such as lymphangitic carcinomatosis, infection, allergy, cardiogenic oedema, or pulmonary haemorrhage. In the presence of confirmatory HRCT scans where other causes of respiratory symptoms have been excluded, a diagnosis of pneumonitis/ILD should be considered and the TMGs ([Table 15](#)) should be followed.

Additionally, when pneumonitis/ILD is suspected during study treatment, the following markers should be measured where possible:

- ILD markers (KL-6, SP-D) and β-D-glucan
- Tumour markers: applicable tumour markers that are related to disease progression
- Additional clinical chemistry: C-reactive protein, lactate dehydrogenase

#### **8.4.6.2 Ophthalmological Examinations**

An ophthalmic assessment, including visual acuity testing, slit lamp examination, intraocular pressure measurement, fundoscopy, and fluorescein staining will be performed at screening and at the end of treatment visit. The assessment should also be performed any time during the study if a participant experiences any visual symptoms (including blurring of vision), with additional tests if clinically indicated. Any clinically significant findings, including those confirmed by an ophthalmologist, must be reported as an AE. Photographs should be taken to record any clinically significant findings. Ophthalmology examination results should be recorded in the eCRF.

### **8.5 AEs and SAEs**

The Principal Investigator is responsible for ensuring that all staff involved in the study are familiar with the content of this section.

The definitions of an AE or SAE can be found in [Appendix B](#).

AEs will be reported by the participant.

The Investigator and any designees are responsible for detecting, documenting, and recording events that meet the definition of an AE.

#### **8.5.1 Time Period and Frequency for Collecting AE and SAE Information**

Data on AEs and SAEs will be collected from time of signature of the informed consent form, throughout the Treatment Period and including the 28 or 42-day (+ 14 days) safety follow-up

period. During the extended follow-up period, only data for SAEs will be collected.

SAEs will be recorded from the time of signing of the informed consent form.

If the Investigator becomes aware of an SAE with a suspected causal relationship to the IMP that occurs after the end of the clinical study in a participant treated by him or her, the Investigator shall, without undue delay, report the SAE to the Sponsor.

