At least 3 evaluable participants are required at the optimal dose of FPI-2053 to be taken forward to Part B. At least three, and up to nine, evaluable participants are required for each dose cohort in Part B as per the mTPI-2 design (unless unacceptable toxicity is seen before three evaluable participants). The actual number of dose levels and participants enrolled during dose escalation will depend upon the number of DLTs in each cohort, the dosimetry at each dose level, and the overall safety profile observed, including the emergence of late-onset toxicities, as the study progresses.

Cohorts A1 and A2 will be initiated simultaneously and conducted in parallel. It is estimated that up to 110 participants may be enrolled. It is estimated that 9 participants will be enrolled in Part A, approximately 18 participants in Part B, 20 participants in backfill, and 60 participants at the RP2D.

The estimated study treatment duration for participants is approximately 12 months.

It is estimated that the clinical study will take approximately 4 years to complete.

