Prior to the administration of [Ac]-FPI-2068, all AEs related to [In]-FPI-2107 or FPI-2053 should be resolved to Grade 1 or baseline. A delay of 28 days is acceptable from the time of the last [In]-FPI-2107 ( $\pm$  FPI-2053) administration to the administration of [Ac]-FPI-2068 if an AE related to [In]-FPI-2107 or FPI-2053 requires longer time for resolution. In circumstances (e.g., intercurrent illness, etc.) where a delay of [Ac]-FPI-2068 administration may be necessary, the Sponsor and/or Medical Monitor must be consulted to discuss whether the participant can receive [Ac]-FPI-2068. In this scenario, Sponsor and/or Medical Monitor agreement is required prior to [Ac]-FPI-2068 administration. Laboratory results confirming bone marrow and organ function, within retreatment criteria requirements must be documented within 48 hours prior to each cycle of [Ac]-FPI-2068 administration.

Refer to Sections 8.1.4 through 8.1.7 for the assessment details and timepoints performed, and for the biospecimens and information collected during the Treatment Period.

4. *End of Treatment and 28- or 42-Day (+ 14 days) Safety Follow-Up Period:* Participants who do not receive any [Ac]-FPI-2068 (i.e., those who do not enter the Treatment Period) will have a Day 28 ( $\pm$  3 days) safety visit as their last study visit. Participants who receive treatment with [Ac]-FPI-2068 will have a safety visit on Day 42 (+ 14 days) before entering the Extended Safety Follow-up Period.
5. *Extended Safety Follow-up Period:* Because cumulative radiation exposure may be associated with an increased risk of delayed onset of radiation-induced toxicity, participants will undergo additional safety assessments at 3-month intervals. The Extended Safety Follow-up Period will begin 3 months following the last dose of

[Ac]-FPI-2068, and will continue every 3 months for 2 years, then every 6 months for an additional 3 years up to 5 years, or until the participant withdraws from the study (see Section 7.2). Refer to Section 8.1.8 for the assessment details and timepoints performed, and for the biospecimens and information collected during the Extended Safety Follow-up Period.

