#### **4.4 End of Study Definition**

A participant is considered to have completed the study if they have completed all phases of the study including the last visit as per the Schedule of Activities (SoA) in Section 8.1.

The end of the study is defined as the date of the last visit of the last participant in the study or last scheduled procedure shown in the Schedule of Activities for the last participant in the study globally.

There will be a data cut-off defined as when the last participant dies or 2 years after the final participant discontinues investigational product, whichever is sooner. The primary data analysis, including the OS and PFS analysis will be performed, and a Clinical Study Report (CSR) written based on this data set. Any participants still alive at the time of data cut-off will continue in long-term safety follow-up. The clinical database may be closed at the time of data cut-off and subsequent safety data collected on paper. A safety addendum to the CSR to include the long-term safety data may be prepared.

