### 8.1.8 End of Treatment and Extended Follow-up Period

**Table 25** Schedule of Assessments - End of Treatment and Extended Follow-up Period

Assessments/procedures a	End of Treatment b	42 -Day (+ 14 days) Safety Follow-Up c	Extended Safety Follow-up (after the last dose)	Details in Section/Appendix
	± 3 days	After the last dose (± 3 days)	Every 3 months (± 2 weeks) for 2 years then every 6 months for 3 years	
Subsequent anti-cancer treatment	X	X	X	9.4.2
AE monitoring	X	X	X d	8.5
Concomitant medications and procedures	X	X		6.6
Haematology (whole blood) with blood smear (pathology)	X	X	X	8.4.4
Clinical chemistry (serum or plasma)	X	X	X	8.4.4
Thyroid panel		X		8.4.4
Urinalysis		X		8.4.4
Pregnancy test (blood or urine, in accordance with institutional practice)	X			8.4.4
Complete physical examination	X			8.4.1
Symptom-directed physical examination		X		8.4.1
ECOG Performance Status	X	X		8.4.5
Weight	X			8.4.1
Ophthalmologic examination	X			8.4.6.2
CT or MRI for RECIST 1.1 Response Assessments	X d		X e	8.2
Serum for tumour marker measurement (e.g., CA-19-9, CEA, etc.) g	X		X h	8.8.1.3
Blood for TCR analysis	X		X	8.8.1.1

ADA, anti-drug antibody; AE, adverse event; CA-19-9, carbohydrate antigen-19-9; CEA, carcinoembryonic antigen; CT, computed tomography; ctDNA, circulating tumour DNA; ECOG, Eastern Cooperative Oncology Group; MRI, magnetic resonance imaging; PK, pharmacokinetics; RECIST, Response Evaluation Criteria in Solid Tumours; RNA, ribonucleic acid; TCR, T-cell receptor.

**a** If clinically indicated, any procedure or assessment may be conducted as an unscheduled visit.

**b** The End of Treatment visit should be conducted within 7 days of the decision to permanently discontinue treatment with  $[^{225}\text{Ac}]$ -FPI-2068.

The Follow-up Visits should be scheduled within CSP-defined timeframe (e.g., 42-56 days) based on the date of the last dose of IMP.

d Only related AEs to be collected in the Extended Follow-Up Period.

Only related AEs to be collected in the Extended Follow Up Period.

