### 8.5.9 Reporting of SAEs

All SAEs have to be reported, whether or not considered causally related to the investigational product, or to the study procedure(s). All SAEs will be recorded in the eCRF.

If any SAE occurs in the course of the study, then Investigators or other site personnel inform the appropriate Sponsor representatives within 1 day, i.e., immediately but **no later than 24 hours** of when he or she becomes aware of it.

The designated Sponsor representative works with the Investigator to ensure that all the necessary information is provided to the Sponsor's representative Patient Safety data entry site **within one calendar day** of initial receipt for fatal and life-threatening events **and within 5 calendar days** of initial receipt for all other SAEs.

For fatal or life-threatening AEs where important or relevant information is missing, active follow-up will be undertaken immediately. Investigators or other site personnel will inform Sponsor representatives of any follow-up information on a previously reported SAE within one calendar day, i.e., immediately but **no later than 24 hours** of when he or she becomes aware of it.

Once the Investigators or other site personnel indicate an AE is serious in the electronic data capture (EDC) system, an automated email alert is sent to the designated Sponsor

representative.

If the EDC system is not available, then the Investigator or other study site staff reports a SAE to the appropriate Sponsor representative by telephone.

The Sponsor representative will advise the Investigator/study site staff how to proceed.

The reference document for definition of expectedness for the IMPs in this study can be found in the IB.

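### Section 8.5.1 and the Table 25 footnote set different AE collection rules for extended follow-up, so a related non-serious late toxicity is recorded under one and not the other

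*Protocol*

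**What the plan says.** **AE collection.** Section 8.5.1 collects all AEs and SAEs up to the end of the 28- or 42-day (+14 days) safety follow-up. After that, "During the extended follow-up period, only data for SAEs will be collected". Table 25 (Section 8.1.8) keeps AE monitoring in the extended follow-up column, with the footnote "Only related AEs to be collected in the Extended Follow-Up Period". Section 8.5.9 adds: "All SAEs have to be reported, whether or not considered causally related to the investigational product".

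**Purpose and use of the period.** Section 4.1.4 justifies the extended visits by the risk of delayed radiation toxicity from cumulative exposure. Section 9.4.3 restricts AE summary tables to treatment-emergent events, with a window that closes 28 or 42 (+14) days after the last dose. Later events are listed only.

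**Duration.** Section 4.1: "It is estimated that the clinical study will take approximately 4 years to complete". Section 4.4 ends the study at the last participant's last visit or "last scheduled procedure shown in the Schedule of Activities for the last participant in the study globally". Section 4.1.4 starts extended follow-up 3 months after the last dose, and it "will continue every 3 months for 2 years, then every 6 months for an additional 3 years up to 5 years". Section 4.4 separately sets a data cut-off at the last death or 2 years after the final participant stops investigational product, whichever is sooner. The clinical study report is written on that data set.

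**The concern.** The two AE rules differ in kind, and neither contains the other. A site working from the schedule would enter a related, non-serious late event as an AE. A site working from Section 8.5.1 would not. Nothing says which text prevails. A related late event is what the extended visits are meant to detect, so the late toxicity record could depend on which page a site reads.

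Laboratory tests cover part of the gap, because Table 25 keeps haematology and chemistry at these visits. They do not supply the investigator's causality assessment, the duration or the outcome, and they do not show events such as the skin and eye toxicities that Table 5 names as risks. For eye findings there is a further tension. Section 8.4.6.2 calls for an ophthalmic assessment whenever visual symptoms occur during the study and requires clinically significant findings to be reported as AEs. A non-serious finding during extended follow-up is therefore reportable under 8.4.6.2 and not collected under 8.5.1.

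Separately, the stated study length is shorter than the follow-up scheduled for a single participant.

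**Working it through.** **1. The rules side by side.** Classify a late event by seriousness and relatedness.

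| Late event | 8.5.1 | Table 25 footnote | 8.5.9 | Result |
|---|---|---|---|---|
| Serious, related | collected | collected | reported | agreed |
| Serious, unrelated | collected | not collected | reported | settled by 8.5.9 |
| Non-serious, related | not collected | collected | does not apply | **open** |
| Non-serious, unrelated | not collected | not collected | does not apply | agreed |

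Reading the two rules jointly, so that only related SAEs are collected, fails because 8.5.9 requires unrelated SAEs as well. One cell remains in conflict.

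**2. Visits affected** (schedule from Section 4.1.4 and Table 25, months counted from the last dose).
- Three-monthly for 2 years: months 3, 6, …, 24, so 24 / 3 = 8 visits.
- Six-monthly for 3 more years: months 30, 36, …, 60, so 36 / 6 = 6 visits.
- Total: 8 + 6 = 14 visits per participant who completes follow-up.

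**3. Where these events would appear.** The treatment-emergent window closes at most 42 + 14 = 56 days after the last dose. Extended follow-up starts 3 months after it. Every AE arising in this period therefore falls outside the window and is listed, not tabulated.

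**4. The 4-year figure.** The protocol gives no derivation, so two readings were tried.

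*End of study as Section 4.4 defines it, for one participant who completes follow-up.* Duration = screening + time from first to last dose + 5 years, at 365.25 days per year. Screening is 28 days in Part B (Table 19) and 39 days in Part A (Table 17). Dosing is up to 3 cycles of 56 (+28) days.
- Part B, 1 cycle: 28 d + 5 y = 5.08 y.
- Part B, 3 cycles on time: 28 + 2 × 56 = 140 d; 140 / 365.25 + 5 = 5.38 y.
- Part B, 3 cycles, both intervals extended by 28 days: 28 + 2 × 84 = 196 d; 196 / 365.25 + 5 = 5.54 y.
- Part A, 3 cycles on time: 39 + 112 = 151 d; 151 / 365.25 + 5 = 5.41 y.

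All exceed 4 years before any accrual time is added.

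*Time to data cut-off.* Take 2 years after the final participant's last dose.
- 4 − 2 = 2.00 y is left for accrual and treatment.
- With 112 days of dosing: 2 − 112 / 365.25 = 1.69 y for accrual.
- With 168 days of dosing: 2 − 168 / 365.25 = 1.54 y for accrual.

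Four years is therefore possible as time to cut-off with about 1.5 to 2 years of accrual. It does not fit the Section 4.4 end of study if the last participant completes follow-up.

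**The case against.** **Weight of the AE conflict.** Late AEs are listed only, all SAEs must be reported whatever their cause, Section 8.5.12 makes a death from late-onset toxicity an SAE, and haematology and chemistry continue. All of this stands and keeps the point minor. A reader might infer that the primary safety analysis is compromised, because AE frequency, duration and severity is a primary endpoint. The documents do not support that: the AE summary tables stop at the treatment-emergent window. Nor do the dose-escalation rules use these data, since DLTs are counted in Cycle 1 only. Sections 4.1 and 9.2 do let late-onset toxicity influence the number of dose levels and participants, so a consistent record has some value there, but no decision rule is tied to it. The text of Table 25 at hand is partly broken, yet the footnote sentence itself is legible.

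**Duration.** Section 4.1 is hedged as an estimate. Follow-up can end early through withdrawal or death, and participants have advanced disease with a required life expectancy of only 3 months or more. A reader might infer that the 4-year figure is simply wrong. That goes too far, because it fits the data cut-off. What stands is that 4.1 calls it completion, and Section 4.4 defines the end of the study differently.

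**Data capture after cut-off.** Section 4.4 says "The clinical database may be closed at the time of data cut-off and subsequent safety data collected on paper", while Section 8.5.9 says "All SAEs will be recorded in the eCRF". Section 8.5.12 and Appendix A 7 also point to the eCRF. A reader might infer that late SAEs and deaths have no stated place once the database closes, or that the optional safety addendum breaks the reporting commitments in Section 9. Neither inference holds. Section 4.4 names paper as the place, as a specific and permissive provision beside general recording rules. Section 8.5.9 gives a telephone route when the electronic system is unavailable. Section 4.4 also bases the study report on the cut-off data set, so requiring an addendum would be a preference, not the correction of an error.

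**Conclusion.** The AE conflict holds and is minor. It concerns one class of event, the related non-serious late toxicity, at 14 scheduled visits per participant who completes follow-up. The consequence is an inconsistent late AE listing. SAE reporting, the AE summary tables and the DLT-based dose rules are untouched. This conclusion follows from the wording alone. The visit count assumes that the 5 years run from the last dose.

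The duration point is a secondary labelling matter. A participant who completes all scheduled follow-up takes 5.08 to 5.54 years in Part B, against the 4 stated. The mismatch arises only if someone survives and stays to the end, and it goes away if 4 years is meant as time to the primary data cut-off. Whether that is the sponsor's intent cannot be told from the protocol. How many participants would reach late follow-up cannot be told either, and the conclusion does not depend on it.

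**What to change.** Put one sentence in both Section 8.5.1 and the Table 25 footnote:

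*During extended follow-up, all SAEs, and AEs of any grade considered related to study intervention, will be collected through the last extended follow-up visit.*

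This agrees with Section 8.5.9 and keeps the related non-serious events that the period is meant to detect.

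In Section 4.1, state that the estimate of about 4 years refers to the primary data cut-off, if that is what the sponsor intends. Add that the end of study under Section 4.4 may be up to 5 years after the last participant's last dose.

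The cost is wording in two sections and one footnote. No visit, test or analysis is added. Sites that have followed 8.5.1 would need to record related non-serious late events from then on.
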